6.6.1 Adverse events

Missing or incomplete AE dates are imputed according to BI standards [\(2\)](#).

6.6.2 Laboratory values at baseline

For missing laboratory data at C1V1 (before the very first administration of study medication) data from preceding visits will be used.

6.6.4 Randomisation and stratification (IRT versus CRF) (only for phase II)

In general, data as reported in the eCRF will be used for analyses. If data are missing in the eCRF (e.g. stratification factors) they will be imputed with the data from Interactive Response Technology (IRT).

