## 7.5 RANDOMISATION

No randomisation is needed for the Phase I part. Patients will be assigned sequentially to the dose cohort at the time.

In the Phase II part, patients will be randomised in a 1:1 ratio to one of the two treatment groups. Randomisation will be stratified based on visceral involvement (yes vs. no). Within each stratum, a central randomisation will be performed across all study centres. The method of permuted blocks will be used.

An Interactive Response Technology (IRT) will be used to perform the randomisation centrally. Boehringer Ingelheim will arrange for the randomisation. A randomisation list will be generated using a validated pseudo-random number generator, yielding reproducible and non-predictable results.

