7.4.2 Phase II

The primary analysis will be conducted for all patients of the randomised set in the Phase II part of this trial; following the changes described in [Section 4.2](#), only response assessments until the cut-off date of 25th November 2016 will be used (as described in protocol). For the derivation of the censoring rules, the status of the patient (e.g. treatment ongoing / discontinued / new anti-cancer therapy) will be taken as of the cut-off date. This means if a patient was ongoing at the cut-off date, its PFS with cut-off will be censored at last assessment before the cut-off, with reason treatment ongoing.

PFS by investigator's assessment is the primary endpoint and will be assessed based on the Kaplan-Meier method for each treatment arm separately. Point estimates together with confidence intervals (CIs) (based on Greenwood's method) will be provided for median PFS.

Proprietary confidential information © 2018 Boehringer Ingelheim International GmbH or one or more of its affiliated companies

An estimation of the effect on PFS of xentuzumab plus exemestane plus everolimus compared to the effect on PFS of exemestane and everolimus will be given by the hazard ratio (HR) and its 95% CI using a stratified Cox proportional hazards model (using visceral involvement as stratification factor). The validity of the underlying assumptions of this model will be checked. HRs < 1 will favour treatment with xentuzumab plus exemestane plus everolimus; p-value from the two-sided log-rank test will be also displayed but it should be emphasised here that this is only to be understood in an exploratory way. The Breslow method for handling ties will be used. The censoring rules for PFS are as stated in [Section 5.1.2](#).

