7.4.2.2 Sensitivity analyses for PFS

Using all available data

As a sensitivity analysis, the PFS analysis (without subgroup analysis) will be repeated, using all available radiological response assessment data (including those measured after the cut-off date from the primary analysis). As for the primary analysis, the randomised set will be used.

Stratification factor based on IRT

The PFS analysis will be repeated, using data from IRT stratification (for the factor visceral involvement) instead of using data collected in the CRF. As for the primary analysis, only response assessments until the cut-off date of 25th November 2016 will be used.

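### Breslow ties pull the primary PFS hazard ratio slightly toward 1 with no tie sensitivity analysis planned, and the response models have no version by the randomisation stratum (minor)

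*SAP*

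**What the plan says.** - **Randomisation.** Protocol 7.5 allocates patients 1:1 in permuted blocks within the two strata of visceral involvement, centrally through the IRT.
- **Primary model.** Protocol 7.3.1 asks for a Cox model stratified by visceral involvement. It names neither the source of the stratum value nor a tie method. SAP 7.4.2 repeats the model and adds: "The Breslow method for handling ties will be used".
- **Source of the stratum.** SAP 6.6.4: "In general, data as reported in the eCRF will be used for analyses". The IRT value only fills gaps in the eCRF.
- **Planned check.** SAP 7.4.2.2: "The PFS analysis will be repeated, using data from IRT stratification (for the factor visceral involvement) instead of using data collected in the CRF". This covers PFS only. The logistic models for objective response and disease control in SAP 7.5.2.2 are also adjusted for visceral involvement, and no IRT version is listed for them. No analysis with another tie method is listed.
- **Scan calendar.** The Phase II flow chart (footnote 15) places scans 49-56 days after randomisation, 105-112 days, and so on every 8 weeks to week 48. After that the interval is 12 weeks with wider windows, such as 406-420 days. PFS is counted in actual days (SAP 5.1.2).

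**The concern.** Most PFS events will be progressions found at scheduled scans, so many patients will share an event day. With d events tied at one time, Breslow keeps all d patients in the risk set for each of the d terms; Efron removes them progressively. Breslow therefore biases the log HR toward 0 when ties are large relative to the risk set. The HR is the trial's main result, and nothing planned would reveal how far the tie method moves it.

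On the stratum, SAP 6.1 analyses efficacy by randomised group. The stratum that matches this is the one used to allocate the patient, which is fixed before treatment. The SAP uses it as a check for PFS and not at all for the two response endpoints.

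**Working it through.** **1. The plan's own figures.** Protocol 7.6 uses P(observed HR ≤ c) = Φ[(ln c − ln HR) / (2/√d)]. With d = 90, 2/√90 = 0.211. For HR 0.72 and c = 0.8, ln(0.8/0.72) = 0.105, 0.105/0.211 = 0.50 and Φ = 69.1% (stated: 69%). For c = 0.85, 0.9 and 1.0 the results are 78.5%, 85.5% and 94.0% (stated: 78, 86 and 94%). The protocol's accrual formula gives 24.9, 27.9 and 32.5 months, as in Table 7.6: 3. Neither the tie method nor the stratum source enters these figures.

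**2. Simulation set-up.** 1000 trials per scenario, each fitted both ways.
- From the documents: 150 patients, 1:1 blocks within stratum, median PFS 7.8 and 10.8 months (HR 0.72), the protocol scan calendar, analysis at 90 events. Runs at 60 events were added because recruitment stopped early and the actual event count is not given.
- Assumed: 60% visceral, visceral HR 1.0 to 2.0, 20% of patients subject to loss, 5% of events deaths, 5 to 20% eCRF/IRT disagreement.

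**3. Ties.** Scans are either spread over the protocol window or all placed on the due day (the extreme case).

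| True HR | Scans | Events | Distinct event days | Largest tie in a stratum | HR Breslow | HR Efron | P(HR ≤ 0.8), Breslow / Efron |
|---|---|---|---|---|---|---|---|
| 0.72 | spread | 90 | about 51 | about 4 | 0.725 | 0.723 | 67.5% / 67.8% |
| 0.72 | due day | 90 | 14 | about 14 | 0.743 | 0.728 | 64.0% / 66.8% |
| 0.72 | due day | 60 | 10 | about 13 | 0.727 | 0.711 | 66.1% / 67.7% |
| 0.50 | spread | 90 | 55 | about 4 | 0.506 | 0.504 | 98.3% / 98.3% |
| 0.50 | due day | 90 | 15 | about 13 | 0.518 | 0.498 | 98.6% / 98.8% |
| 1.00 | spread | 90 | 48 | about 4 | 1.000 | 1.000 | 15.6% / 16.0% |

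At true HR 0.72 and 90 events, the log-scale difference is ln(0.725/0.723) = 0.003 with spread scans, about 1% of a standard error of 0.21. In the extreme case it is ln(0.743/0.728) = 0.020, about 10% of a standard error. Where there is an effect, the pull is toward 1.

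**4. Stratum source.** Efron fits, true HR 0.72, 90 events; d is the within-trial difference in log HR.

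| Visceral HR | Disagreement | HR by IRT | HR by eCRF | Mean \|d\| | 90th percentile of \|d\| |
|---|---|---|---|---|---|
| 1.0 | 5% | 0.718 | 0.718 | 0.012 | 0.026 |
| 1.0 | 20% | 0.724 | 0.724 | 0.023 | 0.049 |
| 1.5 | 10% | 0.719 | 0.719 | 0.023 | 0.051 |
| 2.0 | 10% | 0.721 | 0.726 | 0.033 | 0.071 |
| 2.0 | 20% | 0.730 | 0.738 | 0.042 | 0.086 |

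Across all scenarios the mean HR differs by 0.000 to 0.008. Nominal type I error at true HR 1 is about 4 to 6% with either source. The 0.008 arises only with a strongly prognostic factor and 20% disagreement, and the simulation treats the IRT value as correct.

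**The case against.** **The effect is too small to matter.** No formal test is planned (Protocol 7.1), inference rests on the size of the observed difference (Protocol 7.2), and the p-value is exploratory (SAP 7.4.2). Under spread windows the tie effect is in the third decimal and conservative. Unscheduled scans, end-of-treatment scans and deaths break up ties further. This stands, and it limits the point to minor. The more flexible imaging of amendment 3 (SAP 5.1.2) helps less: it is dated 15 December 2016, after the 25 November 2016 cut-off for the primary PFS data.

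**The eCRF choice is defensible and already checked.** It contradicts nothing in the protocol, it corrects IRT entry errors, and PFS by IRT stratum will be reported. This stands for PFS. It does not cover objective response or disease control.

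**Stronger readings that the documents do not support.**
- A reader might infer that, in an open-label trial, the eCRF stratum could be recoded after later scans and so bias the HR. Metastatic sites are recorded as at study entry (Protocol 5.3.4), and baseline tumour evaluation must rest on scans within 28 days before treatment (SAP 6.7.1). Nothing shows or suggests recoding driven by outcome.
- A reader might infer that heavy ties distort the primary HR. That needs nearly all scans on the due day, and even then the shift is about a tenth of a standard error.
- A reader might call the change free. It needs no new data, but the current SAP is dated 25 April 2018, after the cut-off. A silent switch of the primary specification would itself be post hoc.

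**Conclusion.** The point holds as a minor one. Breslow is the cruder approximation for scan-driven PFS dates. At true HR 0.72 and 90 events it moves the HR toward 1 by about 0.002 with scans spread over the protocol window, and by about 0.015 if all fall on the due day. The plan has no analysis that would show this. Use of the eCRF stratum causes no demonstrated bias: the mean HR changes by at most 0.008, and a single trial's log HR moves by 0.01 to 0.04 on average, against a standard error of about 0.21. The remaining gap is the missing IRT version for objective response and disease control.

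The sizes rest on the assumed visceral share, visceral HR, disagreement rate and loss. The documents give none of these, nor the actual event count or spread of scan days. No conclusion of the trial is likely to turn on either choice.

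**What to change.** - **Ties (SAP 7.4.2).** Replace Breslow by Efron for the Cox models. If the primary specification is treated as locked, keep Breslow and add an Efron run to SAP 7.4.2.2 as a labelled sensitivity analysis.
- **Stratum (SAP 6.6.4, 7.4.2 and 7.5.2.2).** Analyse by the IRT stratum as randomised, with the eCRF value as the sensitivity analysis. At least, add IRT-stratum models for objective response and disease control, and report the number of IRT/eCRF disagreements by arm.
- **Record.** Date the change in the SAP history table and state that it was made after the 25 November 2016 cut-off.

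Cost: one software option for ties. For PFS, a swap of two analyses that are already planned; for objective response and disease control, two added model fits. No new data are needed. The downside of the IRT stratum is that an entry error leaves a patient in the wrong stratum, which the eCRF sensitivity analysis and the disagreement count would show.

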6.6.5 ECG

If replicate ECG recordings are missing, the arithmetic means per time point will be computed with the reduced (1 or 2) number of recordings.

If single cardiac cycles (also denoted as beats or waveforms) are missing, the arithmetic means per single ECG will be computed with the reduced (1 or 2) number of cardiac cycles.

If baseline is missing, a QTcF/QT interval > 500 msec at any time on treatment will be a notable finding. In case of a missing qualitative ECG finding at baseline, a finding observed on-treatment will be categorized as 'new onset'.

Exposure-response analyses

Missing xentuzumab plasma concentration data, identified in the ADPC dataset by below lower limit of quantification (BLQ), will be replaced by zero if measured at baseline and by $\frac{1}{2}$ lower limit of quantification (LLOQ) if measured on-treatment.

If the actual sampling time of the blood sample or of the ECG recording is not available, the pair of plasma concentration and time-matched ECG endpoint will be excluded from the analyses at the corresponding planned time point. Furthermore, all plasma concentrations flagged with 'exclusion' by the PKEXC variable ADPC dataset will be excluded from the exposure-response analyses.

6.7 BASELINE, TIME WINDOWS, AND CALCULATED VISITS

6.7.1 Baseline

The last measurement observed prior to start of trial medication will be assigned to baseline. Note that for some trial procedures (for example body weight, vital signs, laboratory tests) this may be the value measured on the same day trial medication was started. In these cases it will be assumed that the measurements were taken prior to the intake of any study medication. For tumour assessment, baseline evaluations must be based on Magnetic Resonance Imaging (MRI) or Computed Tomography scans performed no more than 28 days prior to start of trial medication.

Study days and visits will be labelled according to the flow chart of the CTP.

Proprietary confidential information © 2018 Boehringer Ingelheim International GmbH or one or more of its affiliated companies

Unless otherwise specified, baseline is defined as the latest time-point before the very first administration of any study medication. The run-in period in the Phase Ib part is considered as time with study medication. If this criterion is not fulfilled then no baseline will be derived, except in the following case: if a patient is entered (phase Ib part) or randomised (phase II part), but not treated, the last value we have for the patient is considered baseline.

Laboratory values:

Baseline is defined as the latest time-point before the very first administration of any study medication.

If any of these times are missing and the date of laboratory value is equal to the date of first study drug administration, then the laboratory assessment will be considered as according to protocol, i.e. as prior to first study medication.

ECG

Baseline values will be derived from the triplicate at the time-point closest to but prior to the first administration of study medication.

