#### 6.2.2.2 Phase II part

Refer to the [Flow Chart](#) and Appendix 10.5 Tables [10.5.2: 1 – 10.5.2: 2](#) for details including timing on ECG, PK and drug administration.

If extremely necessary, for arm 2 patients receiving BI 836845 infusion at a subsequent visit, the transaction with the IVRS/IWRS system can be done up to one day before the actual visit date. Please refer to BI 836845 Preparation Storage and Administration instructions for more information about BI 836845 stability and storage conditions once diluted in the infusion bag

*Course 1, Visit 1 (Day 1 of 1st treatment course)*

All procedures must be completed on Day 1 of Course 1. However, the randomization may take place up to 3 days prior to the C1V1 if site procedures require advance randomization to accommodate the logistics of dispensing study medication to patients. Sites that use this option must include a copy of the policy or a documented justification in the ISF and submit a copy to the sponsor. The patient must take the first oral dose of study medications and receive BI 836845 infusion (if randomized to BI 836845 containing arm), while she is still at the investigative site, and to record this in the site source document. Sufficient drugs (everolimus and exemestane) should be made available for the patient. Blood samples for biomarkers (for all patients), immunogenicity and PK (for arm 2 patients only) will be collected before (-0.05h) and after (form arm 2 patients only) the administration of everolimus and exemestane with or without BI 836845. ECG will be collected from all patients, prior to trough PK sampling and administration of any study drug, and immediately after the end of BI 836845 infusion (for patients receiving BI 836845) OR one hour after the administration of everolimus + exemestane (for patients not receiving BI 836845).

*Course 1, Visit 2 (8 ±2 Day after C1V1)*

BI 836845 should be administrated with PK blood samples taken before and after the infusion for patients on arm 2 only. ECG, vital signs, adverse events and concomitant medication will be collected from all patients.

*Course 1, Visit 3 (15 ±2 Days after C1V1)*

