- If the overall response is SD, Non-CR/Non-PD, PR, CR or NE, the latest of multiple assessment dates will be taken, i.e. in the case of SD, Non-CR/Non-PD, PR, CR, the latest of multiple dates will be used to censor the patients.

Imaging assessments for which NE is assigned as the overall response at an imaging time-point are considered to be missed assessments. Please note that NE does not indicate lack of progression.

Table 5.1.2: 1 Derivation rules for PFS

Situation	Outcome (event or censored)	Date of outcome
No baseline radiological assessment		
Patient with death on or before the second planned radiological assessment	Event	Date of death

Proprietary confidential information © 2018 Boehringer Ingelheim International GmbH or one or more of its affiliated companies

Table 5.1.2: 1 Derivation rules for PFS (cont.)

Situation	Outcome (event or censored)	Date of outcome
Patient without death or patient with death after second performed radiological assessment	Censored	Date of randomisation (or first treatment administration, in non-randomised trials)
Without post-baseline radiological assessments		
Vital status is unknown or patient is known to be alive	Censored	Date of randomisation (or first treatment administration, in non-randomised trials)
Death prior or on the second planned radiological assessment	Event	Date of death
Death beyond the second planned radiological assessment	Censored	Date of randomisation (or first treatment administration, in non-randomised trials)
With baseline and post-baseline radiological assessments BUT no other anti-cancer therapy		
Alive and not progressed, no more than one consecutively missed radiological assessments	Censored	Date of last radiological assessment
Alive and not progressed, two or more consecutively missed radiological assessments	Censored	Date of last radiological assessment prior to missed radiological assessments
Progressed, zero or one missed radiological assessment prior to progression	Event	Date of radiological assessment of progression

Proprietary confidential information © 2018 Boehringer Ingelheim International GmbH or one or more of its affiliated companies

Table 5.1.2: 1 Derivation rules for PFS (cont.)

Situation	Outcome (event or censored)	Date of outcome
Progressed, but two or more consecutively missed radiological assessments prior to progression	Censored	Date of last radiological assessment prior to missed assessment

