6.2 IMPORTANT PROTOCOL VIOLATIONS

No per protocol set (PPS) analysis will be performed for this study, hence, no patient will be excluded from the analyses (except those with missing informed consent or not adhering to age limit). However patients with potentially important protocol violations (IPVs) will be documented. The following list of potentially IPVs in Table 6.2: 1 will be used; note that this is a working list and may not be finalised until the final Blinded Report Planning Meeting (BRPM) or DBL meeting (but prior to DBL for the primary analysis). Potentially IPVs will be handled according to BI standards [\(6\)](#).

During the study conduct, protocol deviation should be monitored and guidance for improving / teaching the respective sites should be discussed during the study Medical Quality Review Meetings (MQRMs).

Table 6.2: 1 Important protocol violations

Category/ Code		Description	Requirements	Excluded from
A [1]		Entrance criteria not met		
	A1	Diagnosis of trial disease questionable	Inclusion criteria* IN 1 or IN 2 not met.	None

Proprietary confidential information © 2018 Boehringer Ingelheim International GmbH or one or more of its affiliated companies

Table 6.2 : 1 Important protocol violations (cont.)

Category/ Code	Description	Requirements	Excluded from
	A2	Prohibited baseline condition, diagnosis or treatment At least one of inclusion criteria* IN 4- 9 or IN 12 is not met or At least one of exclusion criteria* is met.	None
	A3	Laboratory result indicating inadequate organ function at screening	Inclusion criteria* IN 10 or IN 11 not met
	A4	Adequate archival tumour tissue not available	Inclusion criterion* IN 3 not met.
B [1]		Legal Criteria	
	B1	Informed consent not available / not done	Informed consent date missing or inclusion criterion* IN 13 not met
	B2	Informed consent too late	Informed consent date was after Screening Visit date
	B3	Age limit for patient inclusion not adhered to	Calculate age given the date of birth and date of informed consent. Patients must be ≥ 18 years old.
C		Trial medication and randomisation	
	C1 [2]	Time window violation for procedures performed at screening	Screening imaging earlier than 28 days to first drug intake; Safety labs, ECG performed earlier than 28 days to, or later than first drug intake; Timeframe > 4 days between randomisation and first drug intake

Proprietary confidential information © 2018 Boehringer Ingelheim International GmbH or one or more of its affiliated companies

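### SAP 6.7.1 leaves open whether a screening scan older than 28 days counts as tumour baseline; on one reading a documented progression becomes a day-1 censoring in PFS and TTP

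*SAP*

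**What the plan says.** SAP 6.7.1 opens with a general rule: "The last measurement observed prior to start of trial medication will be assigned to baseline". The same paragraph ends with a rule for tumour assessment, where the baseline "must be based on Magnetic Resonance Imaging (MRI) or Computed Tomography scans performed no more than 28 days prior to start of trial medication". Two paragraphs later the section defines baseline, unless otherwise specified, as the latest time-point before the very first dose, and adds: "If this criterion is not fulfilled then no baseline will be derived". One exception follows: for a patient randomised but not treated, "the last value we have for the patient is considered baseline".

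Table 5.1.2: 1 (SAP 5.1.2) starts with a block for patients who have no baseline radiological assessment. It has two rows. "Patient with death on or before the second planned radiological assessment" is an event at the date of death. "Patient without death or patient with death after second performed radiological assessment" is censored at the date of randomisation. Table 5.2.2.2: 1 censors TTP at randomisation for every patient without a baseline assessment and has no row for death.

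SAP 6.2 takes the same deviation from another side. Table 6.2: 1 lists screening imaging done more than 28 days before first drug intake under violation C1. The introduction to that section says there is no per-protocol analysis and "hence, no patient will be excluded from the analyses", with missing consent and the age limit as the only exceptions.

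The protocol (flow chart footnotes, sections 5.1.2.1 and 6.1) also counts the 28 days back from the start of treatment. Protocol 6.2.2.2 adds that "the randomization may take place up to 3 days prior to the C1V1" where site procedures need it.

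**The concern.** The 28-day sentence stands in the section that defines baseline for analysis, and it is the specific rule for tumour assessment. The general rule applies only where nothing else is specified. A programmer who takes it literally will not accept a scan from 30 days before first dose, will find no tumour baseline, and will go to the no-baseline block. A second programmer who starts from the violation list will keep the scan and flag C1. The two would derive different primary-endpoint outcomes for the same patient.

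On the literal reading the loss for that patient is nearly complete. Censored on day 1, she remains in the randomised set but adds no event, and she has left every Cox risk set after day 1. A timing deviation of one or two days would then outweigh months of scans in an analysis that SAP 6.1 describes as intent-to-treat. The reading also gives an odd ordering: a randomised patient who was never treated keeps her last scan as baseline, while a treated patient with a slightly late scan may have none.

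**Working it through.** **1. One patient, two derivations.** Take a treated patient with a screening CT 30 days before first dose, first dose on the day of randomisation, scans on schedule, no new therapy, and progression on day 169 (the week-24 due date in Table 6.7.2: 1). SAP 5.1.2 gives PFS = date of outcome − date of randomisation + 1, and months = days × 12 ÷ 365.25.

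- Scan accepted as baseline: event, PFS = 169 days = 169 × 12 ÷ 365.25 = 5.6 months.
- Scan not accepted: censored, PFS = 0 + 1 = 1 day = 0.03 months. TTP gives the same.
- Scan not accepted, but death by the second planned assessment (week 16): still a PFS event at the date of death. In TTP she is censored at randomisation.

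**2. Does the text decide between them?** The 28-day rule is worded as a requirement, which favours non-acceptance. The statement that no baseline is derived follows the pre-first-dose definition directly, and a day −30 scan meets that definition, which favours acceptance. C1 names the case and only documents it. No sentence assigns an out-of-window scan to a row of either table.

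**3. Would a planned sensitivity analysis show the effect?** SAP 7.4.2.2 has two. One uses all data after the cut-off date, and the other takes the stratification factor from IRT. Neither changes the baseline rule.

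**4. The plan's own figures.** Protocol 7.6 gives the chance of observing HR ≤ 0.8 with 90 events as 69% if the true HR is 0.72 and 14% if it is 1.0. With 1:1 allocation, P = Φ[(ln 0.8 − ln HR) × √D ÷ 2]:

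- HR 0.72, D = 90: Φ(0.1054 × 4.743) = Φ(0.500) = 69.1%.
- HR 1.0, D = 90: Φ(−0.2231 × 4.743) = Φ(−1.058) = 14.5%.

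Both agree with the table.

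**5. Size under the literal reading.** Inputs: 150 patients and 90 events (protocol 7.3.1), so an event rate of 90 ÷ 150 = 60%. The share q of patients with a scan older than 28 days is not in the documents and is assumed. No early death is assumed to be kept as an event, so the loss is an upper figure for each q. Events lost = 150 × q × 0.60.

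| q (assumed) | Patients | Events lost | Events left | P(HR ≤ 0.8), true HR 0.72 | P(HR ≤ 0.8), true HR 1.0 |
|---|---|---|---|---|---|
| 0 | 0 | 0 | 90 | 69.1% | 14.5% |
| 2% | 3 | 1.8 | 88.2 | 69.0% | 14.7% |
| 5% | 7.5 | 4.5 | 85.5 | 68.7% | 15.1% |
| 10% | 15 | 9.0 | 81.0 | 68.2% | 15.8% |

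The SAP analyses PFS to a fixed date, 25 November 2016, after recruitment was stopped. Events lost in this way would not be made up by longer follow-up, as they would in an event-driven readout. The event count at that date is not given.

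**The case against.** The strongest reply is that the SAP never states the chain. The sentence on deriving no baseline most directly refers to having a measurement before first dose, not to the 28-day limit. The no-baseline rows speak of an absent assessment, not an out-of-window one. Where the SAP names the early scan, in C1, it only documents it, which is close to the fix proposed here. All of this stands. It shows that the text can be read in the harmless way, but it does not remove the tumour-specific requirement or say which rule governs.

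A reader might also infer more than the documents support:

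- *All follow-up is deleted.* It is not. Death by the second planned assessment stays a PFS event, and overall survival uses all available data (SAP 7).
- *The censoring contradicts the promise of no exclusions.* Not literally. A censored patient stays in the analysis set, and SAP 6.2 has its two exceptions. The practical effect on PFS is close to exclusion, but the sentence is not breached.
- *Advance randomisation makes late scans a normal event.* A scan 27 days before randomisation with first dose 3 days later is 27 + 3 = 30 days old. That already breaks the protocol's own limit, which runs to the start of treatment.
- *The loss would differ by arm because only Arm 2 has infusions.* Protocol 6.2.2.2 has patients in both arms take the first oral dose at the site, and advance randomisation is offered for dispensing study medication in general. Nothing shows an arm-related delay.

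**Conclusion.** The point holds as an unresolved conflict between the baseline rule and the violation list, with a severe result for an individual patient on one reading. A treated patient with a screening scan slightly older than 28 days can be censored at randomisation for PFS, unless she dies by the second planned assessment, and for TTP in any case, despite a later documented progression. This follows from reading SAP 6.7.1 with the two derivation tables; no single passage says it.

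The effect on the trial is probably small. About 2 to 5 of 90 planned events are at stake if 2 to 5% of 150 patients are affected and 60% have an event. At 5% the chance of observing HR ≤ 0.8 under a true HR of 0.72 falls from 69.1% to 68.7%. The share is an assumption and the event rate is the protocol's plan, not the count at the cut-off. The trial plans no formal test, so what matters is the estimate. The change is worth making because the rule affects the primary endpoint, no planned analysis would reveal its effect, and it is cheap to settle.

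**What to change.** In SAP 6.7.1, define the tumour baseline as the last adequate CT or MRI before first dose, or the last available scan for a patient randomised but not treated. State that a scan older than 28 days is recorded as violation C1 only. In Tables 5.1.2: 1 and 5.2.2.2: 1, reserve the no-baseline rows for patients with no pre-treatment CT or MRI. If the strict 28-day rule is of interest, repeat PFS with it as a sensitivity analysis and report how many patients change status.

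The cost is one or two sentences, a derivation flag and, if wanted, one extra run. The downside is small but real: with an older baseline, some growth before treatment may count towards progression. The protocol's 28-day requirement for sites does not change.
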